## 14 SAFETY ANALYSIS

The safety analyses will be performed using the safety population.

### 14.1 Adverse Events

Adverse events will be classified using the Medical Dictionary for Drug Regulatory Activities (MedDRA) classification system. The severity of the toxicities will be graded according to the NCI CTCAE whenever possible. Treatment-emergent adverse events (TEAEs) are defined as AEs with onset date on or after the date of first dose of study medication until the date of the last study medication dose plus 28 days. Adverse events will be considered treatment-emergent if all or part of the date of onset of the adverse event is missing and it cannot be determined if the adverse event meets the definition for treatment-emergent.

The number and percentage of patients who experienced TEAEs for each system organ class and preferred term will be presented. Multiple instances of the TEAE in each system organ class and multiple occurrences of the same preferred term are counted only once per patient. The number and percentage of patients with at least one TEAE will also be summarized.

Separate tables will be presented as follows:

- All TEAEs;
- TEAEs by CTCAE grade;
- Grade 3 or greater TEAEs;
- Treatment-related TEAEs;
- Serious TEAEs;
- Serious treatment-related TEAEs;
- TEAEs with an outcome of death;
- TEAEs leading to discontinuation of study medication; and
- TEAEs resulting in reduction, delay, or interruption of study medication
- Time to the first adverse event that results in a reduction, interruption or discontinuation of study drug.

The incidence of TEAEs will be summarized by relationship to study drug according to the following categories: “treatment-related,” or “not treatment-related”. The category of treatment-related is defined as a relationship of “Possible/Probable”, “Definitely”, or missing. If a patient experiences multiple occurrences of the same AE with different relationship categories, the patient will be counted once, as a relationship category of treatment related.

If a patient experiences multiple occurrences of the same AE with different toxicity grades, the patient will be counted once for the maximum (most severe) toxicity grade. AEs with a missing toxicity grade will be presented in the summary table with a toxicity grade of “Missing.” For each toxicity grade, the number and percentage of patients with at least one TEAE of the given grade will be summarized.

The time to the first adverse event that results in a dose reduction, interruption or discontinuation of study drug is defined as 1+ the number of days from the first dose of study drug to the start of the first adverse event. Patients without an event will be censored on the date of their most recent visit date.

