**Table 11: Protocol CO-1686-008 Schedule of Assessments – Phase 2: All Patients**

Procedure b	Screening	Treatment Period							Post- Treatment	
	Day -28 to Day -1	Cycle 1 Day 1 c	Cycle 1 Day 4 ±1 day	Cycle 1 Day 8 ±1 day	Cycle 1 Day 15	Cycle 2 and Beyond Day 1	Cycle 2 Day 15 ±1 day	End of Treatment (28±7 days after last dose)	Follow-Up Every 8 ±1 weeks after EOT	
Informed Consent*	X									
Medical/Oncology History	X									
Physical Examination	X	X			X	X		X		
ECOG Performance Status	X	X				X		X		
Vital Signs d and Weight	X	X			X	X		X		
Prior/Concomitant Medications and Procedures	X	X			X	X		X		
Contraceptive Counseling e	X							X		
Serum Pregnancy Test f	X							X		
Hematology, Including Reticulocytes g	X	X			X	X		X		
Fasting Serum Chemistry h	X	X	Fasting glucose only	Fasting glucose only	X	X	Fasting glucose only	X		
Urinalysis i	X									
Tumor Scans, Including Brain Imaging j	X					X		X		
Tumor/Metastasis Biopsy for T790M Status k	X							X		
Blood for biomarker/EGFR Mutational Testing and exploratory research l	X	X			X	X		X		
Blood for CYP Evaluation (Optional Sampling)		X								
Adverse Events m	X	X			X	X		X		

Procedure b	Screening	Treatment Period							Post- Treatment	
		Day -28to Day -1	Cycle 1 Day 1 c	Cycle 1 Day 4 ±1 day	Cycle 1 Day 8 ±1 day	Cycle 1 Day 15	Cycle 2 and Beyond Day 1	Cycle 2 Day 15 ±1 day	End of Treatment (28±7 days after last dose)	Follow-Up Every 8±1 weeks after EOT
CO-1686 Dispensing / Administration			X			X	X			
Patient Diary n			Dispense Diary			X	X		X	
ECG Assessments o	X	X			X	X			X	
Quality of Life Questionnaires p			X				X		X	
Plasma PK and Serum AAG Samples (Table 12)			X			X	X			
Metabolite Profiling (Table 12)			X			X				
Optional: Urine collection for biomarker research q			X				X		X	
Subsequent Therapies for NSCLC									X	X

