### **2.3.1 Schedule of Assessments**

The procedures and assessments to be performed during the study are outlined in the Schedule of Evaluations in the protocol.

Patients in the Phase 2 portion of this study will receive CO-1686 at 500 mg BID, 625 mg BID or 750 mg BID. Treatment will continue until disease progression, patient withdraws consent for further treatment, or by investigator decision. Treatment can continue post-progression if, in the opinion of the investigator and approved by the sponsor, the patient has indolent progression with evidence of continued clinical benefit from treatment. The study consists of screening, treatment, and follow-up periods.

Within 28 days prior to Cycle 1 Day 1, patients will be screened and evaluated for eligibility for the study. During the treatment period, patients will return to the clinic for study drug and to be evaluated for safety and dosing compliance. Each cycle consists of 21 days. Imaging will be done at the end of Cycles 2, 4, and 6 (between Days 14 and 21) and every 3 cycles after Cycle 6 (between Days 14 and 21).

During the follow-up period, patients will be followed for survival, related serious adverse events (SAEs) and next therapy for NSCLC every 2 months until lost to follow-up, withdrawal of informed consent or sponsor decision. The follow-up data may be collected by visit, telephone or chart review.

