### 3 GENERAL ANALYSIS CONVENTIONS

The summary tables will be presented for all patients treated with at least one dose of CO-1686 (safety population). Particular dose groups of interest, including patients from both Phase 1 and Phase 2, may be presented in the summary tables.

Quantitative variables will be summarized using descriptive statistics and may also be summarized categorically with frequencies and percentages. For variables registered on a continuous scale, the following will be presented: N, mean, standard deviation, median, minimum and maximum. Categorical variables will be presented using frequencies and percentages and the randomized treatment groups may be compared using Fisher's exact test. The Kaplan-Meier methodology will be used to summarize time-to-event variables. If estimable, the median together with a 95% confidence interval will be presented. The number of patients with events and the number of censored patients will also be presented.

All data will be used to their maximum possible extent but without any imputations for missing data.

Unless otherwise specified, baseline is defined as the last measurement on or prior to the first day of study drug administration.

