## 14.2 Clinical Laboratory Evaluations

Clinical laboratory evaluations include the continuous variables for hematology, serum chemistry, and urinalysis. The on-treatment period will be defined as the time from the first dose of study drug to 28 days after the last dose of study drug. Laboratory values collected during the on-treatment period will be included in the summary tables.

The summary of laboratory data will include descriptive statistics (N, mean, StDev, minimum, median, and maximum) of the maximum, minimum and last value during the on-treatment period. Summaries using descriptive statistics of the change from baseline to the maximum, minimum, and last value during the on-treatment period will also be given.

Shift tables from baseline to the worst CTCAE grade on-treatment will also be summarized.

Graphs of the mean values over time may also be provided.

Glucose values will also be stratified into categories indicative of clinical significance. Each patient's maximum glucose value on treatment will be classified as

- >200 mg/dL
- >250 mg/dL
- >500 mg/dL.

The frequency of patients that achieve each of these levels at least 1 time or at least 2 times will be summarized.

The time to the initial use of a glucose lowering concomitant medication will be summarized with Kaplan-meier methodology. Patients that have not taken any glucose lowering medications will be censored on the last visit date.

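### Censoring the time to a dose-changing adverse event at the last visit keeps patients at risk after CO-1686 has stopped, so the curve understates on-drug risk

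*SAP*

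**What the plan says.** SAP 14.1 sets out a time to the first adverse event leading to dose reduction, interruption or discontinuation. SAP 15 lists it among the additions to the protocol analyses. The time "is defined as 1+ the number of days from the first dose of study drug to the start of the first adverse event", and for everyone else "Patients without an event will be censored on the date of their most recent visit date". Section 14.1 names no estimator, but the general convention in SAP 3 does: "The Kaplan-Meier methodology will be used to summarize time-to-event variables".

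SAP 14.2 sets out a Kaplan-Meier analysis of time to first glucose-lowering medication: "Patients that have not taken any glucose lowering medications will be censored on the last visit date".

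Neither section says which contacts count as a visit, and nothing limits either endpoint to time on drug. After the last dose the protocol schedules an End of Treatment visit 28 (±7) days later (section 9.6 and Table 11). After that, according to SAP 2.3.1, "patients will be followed for survival, related serious adverse events (SAEs) and next therapy for NSCLC every 2 months", and "The follow-up data may be collected by visit, telephone or chart review".

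The SAP has suitable end dates but does not use them here. Treatment-emergent AEs (14.1) and on-treatment laboratory values (14.2) end 28 days after last dose, and time to treatment failure (11.3.2) ends at last dose.

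**The concern.** An adverse event cannot change the dosing of a drug that the patient no longer takes. Under the 14.1 rule, a patient who stops for progression is nevertheless counted as at risk, and event-free, until the last visit. Each such patient enlarges the denominator without being able to contribute an event.

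The result is hard to interpret. It is not the risk while on drug, because off-drug time is mixed in. Nor is it the proportion of treated patients who have the event, because stopping for other reasons is not handled as a competing event. The amount of off-drug time depends on which contacts are programmed as visits.

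The SAP is written for the NDA and MAA (section 1), and dose-changing toxicity is common with this drug. Protocol Appendix D, Table 1 shows Grade 3 or greater hyperglycemia in 131 + 66 + 13 = 210 of 635 patients (33%). A reader of the submission would probably take the curve as tolerability on treatment.

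**Working it through.** **No figure to reproduce.** The documents give no expected event rate or Kaplan-Meier value for either endpoint. The direction follows from the formula; the size has to be illustrated on assumptions.

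**Direction.** The estimated risk is 1 − Π(1 − dᵢ/nᵢ), where dᵢ is the number of events and nᵢ the number at risk at each event time. If mᵢ of the nᵢ are already off drug and cannot have an event, the SAP rule uses dᵢ/nᵢ where the on-drug hazard is dᵢ/(nᵢ − mᵢ). Each factor is then too close to 1, and the estimated on-drug risk is too low.

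**Inputs from the documents.** Visits every 21 days; End of Treatment at last dose + 28 ± 7 days; follow-up every 8 weeks (protocol Table 11); enrolment to 31 December 2014 and cutoff on 29 April 2015 for 500 and 625 mg BID (SAP 2.4), so at least 119 days of potential follow-up.

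**Assumed, not in the documents.** On-drug event risk by day 21 of 10% or 30%; later on-drug events with a median of 180 or 365 days; non-AE discontinuation with a median of 120, 180 or 270 days; median survival after stopping of 300 days; uniform enrolment over 180 days; no events off drug. This gives 2 × 2 × 3 = 12 scenarios, each with 400,000 simulated patients.

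**Results at day 168 (%)** for the scenarios with the largest and smallest shortfalls:

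| Day-21 risk / later median / discontinuation median | Last dose | End of Treatment | Last follow-up visit | Cumulative incidence |
|---|---|---|---|---|
| 10% / 180 d / 120 d | 49.7 | 44.8 | 36.2 | 33.6 |
| 10% / 365 d / 270 d | 32.4 | 30.9 | 28.5 | 27.2 |
| 30% / 365 d / 270 d | 47.3 | 45.7 | 43.7 | 42.7 |

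The first three result columns are 1 − KM under that censoring date; the last treats non-AE discontinuation as a competing event.

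- End of Treatment as last visit: shortfall against last-dose censoring of 32.4 − 30.9 = 1.5 to 49.7 − 44.8 = 4.9 points.
- Follow-up visits counted: 47.3 − 43.7 = 3.6 to 49.7 − 36.2 = 13.5 points.
- At day 84 the corresponding ranges are 0.9 to 3.2 and 1.4 to 4.9 points.

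The simulated true on-drug risk is slightly below the last-dose column (49.0 against 49.7 in the first row), because patients still on drug were censored at their last 21-day visit. Against the true value the worst shortfalls are 49.0 − 44.8 = 4.2 and 49.0 − 36.2 = 12.8 points.

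**Check against cumulative incidence.** In all 12 scenarios the SAP rule lies at or above the cumulative incidence. A closed form agrees. Take constant hazards, 50% on-drug risk at day 180, and a median time to other-cause discontinuation of 4 or 9 months (120 or 270 days). Then λₑ = ln 2/180 = 0.00385 per day, λ_d = ln 2/120 = 0.00578 or ln 2/270 = 0.00257, and the incidence is λₑ/(λₑ + λ_d) × [1 − exp(−180(λₑ + λ_d))]:

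- 120 days: 0.400 × (1 − 0.177) = 0.329
- 270 days: 0.600 × (1 − 0.315) = 0.411

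A separate simulation of that setting (20,000 patients per scenario) gave 44–47% under the SAP rule with End of Treatment as last visit and 35–42% with follow-up visits, against 50% with last-dose censoring. The SAP rule thus falls between the two quantities a reader might want.

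**Glucose endpoint.** Concomitant medications are collected at End of Treatment for the period since the previous visit (protocol 9.6). A start in that interval can therefore occur and be recorded, and up to 28 days after last dose it also lies in the SAP's laboratory window. After End of Treatment, protocol 9.7 lists only later NSCLC treatment and survival, so further time at risk would be unobserved.

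**The case against.** The strongest reply has four parts.

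1. **The target is not stated.** Last-dose censoring answers a question about risk while on drug, and the SAP does not say that this is the question. This stands in part. A reader might infer that the curve understates how many treated patients have a dose-changing event. The documents and the calculation do not support that: the SAP rule is at or above the cumulative incidence throughout. The shortfall is only against on-drug risk. The rule still estimates neither quantity, so the point goes beyond an undefined word.

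2. **The ordinary last visit is End of Treatment.** The protocol keeps that visit apart from follow-up, which may be by telephone (9.7), and SAP 2.3.1 lists visit, telephone and chart review as alternatives. Protocol 5.4 limits two-monthly follow-up to Phase 2, although 9.7 says all patients. This stands: the smaller range is the more likely one, and the larger one needs follow-up visits to count. The shortfall is smaller again for early events, and protocol 7.4.3 says hyperglycemia generally appears in the first 3 weeks. Treatment after progression (5.1.4) also shortens off-drug time.

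3. **The glucose rule is much the same as a sensible one.** This stands under the End of Treatment reading. It would be wrong to call both endpoints equally defective.

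4. **Tolerability does not rest on these curves.** SAP 14.1, 14.2 and 14.4 also tabulate AEs leading to discontinuation or dose change, glucose thresholds and QTc categories, none of which depends on this censoring. This limits the consequence but does not make the curve correct.

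A reader might also infer that dose groups with more early progression would look more tolerable. No calculation here examined that, and the SAP specifies no comparison of dose groups on these curves, so the claim is not made.

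**Conclusion.** The point holds for the AE endpoint in SAP 14.1, as a statement about on-drug risk. The direction follows from the event definition: once CO-1686 has stopped, a dose change is essentially impossible, yet the patient remains at risk. The size is illustrative and modest on the likelier reading of visit, about 1.5 to 5 points at day 168, rising to about 13 points if follow-up visits count. These figures rest on assumed hazards, discontinuation times and survival, since the documents give none. Patients still on drug are not affected.

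For the glucose endpoint in SAP 14.2, the rule is defensible if the last visit is End of Treatment. What is missing is a sentence that keeps later follow-up contacts out of the time at risk.

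**What to change.** - **SAP 14.1:** state that the target is the risk of a dose-changing AE while on CO-1686, and censor event-free patients at the earlier of last dose and data cutoff. The last-dose date is already used in SAP 11.3.2.
- **Optional addition:** an Aalen-Johansen cumulative incidence with non-AE discontinuation and death as competing events. It will give a lower figure than the on-drug curve, and the two should be labelled as answers to different questions.
- **SAP 14.2, glucose-lowering drug:** state that event-free patients are censored at the earlier of last dose + 28 days (or End of Treatment) and data cutoff, so that follow-up contacts add no time at risk.

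The cost is a few sentences and changed censoring dates in two programs, with no new data. The reported on-drug AE risk will look slightly less favourable.

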## 14.2 Clinical Laboratory Evaluations

Clinical laboratory evaluations include the continuous variables for hematology, serum chemistry, and urinalysis. The on-treatment period will be defined as the time from the first dose of study drug to 28 days after the last dose of study drug. Laboratory values collected during the on-treatment period will be included in the summary tables.

The summary of laboratory data will include descriptive statistics (N, mean, StDev, minimum, median, and maximum) of the maximum, minimum and last value during the on-treatment period. Summaries using descriptive statistics of the change from baseline to the maximum, minimum, and last value during the on-treatment period will also be given.

Shift tables from baseline to the worst CTCAE grade on-treatment will also be summarized.

Graphs of the mean values over time may also be provided.

Glucose values will also be stratified into categories indicative of clinical significance. Each patient's maximum glucose value on treatment will be classified as

- >200 mg/dL
- >250 mg/dL
- >500 mg/dL.

The frequency of patients that achieve each of these levels at least 1 time or at least 2 times will be summarized.

The time to the initial use of a glucose lowering concomitant medication will be summarized with Kaplan-meier methodology. Patients that have not taken any glucose lowering medications will be censored on the last visit date.

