#### 11.2.10.3 Clinical Laboratory Evaluations

Clinical laboratory evaluations include the continuous variables for hematology, serum chemistry, and urinalysis. Laboratory values will be presented in Systeme International units. The baseline laboratory value will be defined as the last value prior to or on the day of the first dose of oral CO-1686. The on-treatment period will be defined as the day after the first dose of oral CO-1686 to 28 days after the last dose of CO-1686. Laboratory values collected during the

on-treatment period will be included in the summary tables. The laboratory values collected after the on-treatment period will only be presented in the data listings.

The summary of laboratory data will include descriptive statistics (N, mean, standard deviation, minimum, median, and maximum) of the maximum, minimum, and last value during the treatment period by dose group and study phase. Summaries using descriptive statistics of the change from baseline to the maximum, minimum, and last value during the on-treatment period will also be given by dose group and study phase. Supporting laboratory data including normal ranges and abnormal laboratory flags will be provided using by-patient listings. Separate listings will be produced for clinically significant laboratory abnormalities (i.e., those that meet Grade 3 or 4 criteria according to CTCAE Version 4.0) by dose group.

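### The SAP starts the laboratory and vital-sign on-treatment period at first dose but keeps a baseline that includes Day 1, so a predose Day 1 value counts as both if the window is applied by calendar date.

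*SAP*

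**What the plan says.** **SAP.** Section 3 states that, unless otherwise specified, "baseline is defined as the last measurement on or prior to the first day of study drug administration". Sections 14.2 and 14.3 specify nothing different. For laboratory values, Section 14.2 says "The on-treatment period will be defined as the time from the first dose of study drug to 28 days" after the last dose; Section 14.3 gives the same window for vital signs. Both sections then summarise the maximum, minimum and last on-treatment values and their changes from baseline; in 14.2, "change from baseline to the maximum, minimum, and last value during the on-treatment period will also be given". For laboratory data there is more: "Shift tables from baseline to the worst CTCAE grade on-treatment will also be summarized", and each patient's on-treatment glucose is counted against three thresholds, reached at least once or at least twice.

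**Protocol.** Section 11.2.10.3 has an equivalent baseline: "The baseline laboratory value will be defined as the last value prior to or on the day of the first dose". Its window starts later: "The on-treatment period will be defined as the day after the first dose of oral CO-1686 to 28 days after the last dose". Section 11.2.10.4 repeats both rules for vital signs.

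**Record of changes.** SAP 15 lists six changes from the protocol's analyses. The start of the on-treatment window is not among them.

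**The concern.** Under the protocol, Day 1 belongs to baseline only. The SAP moves the start of the window back to first dose and leaves the baseline where it was, so Day 1 can belong to both.

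Scheduled Day 1 hematology, chemistry and vital signs are taken before dosing (Protocol 9.3.1 and 9.5.1). The value that could be double counted is therefore normally a pre-treatment one. If it enters the on-treatment record, changes to the maximum and minimum are truncated at zero. Worst-grade shifts and glucose threshold counts can also include a measurement made before any drug was taken.

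Patients with few later visits are the most exposed. In Phase 2, after Day 1 the next scheduled hematology, full chemistry and vital signs fall on Day 15; Days 4 and 8 are fasting glucose only (Protocol Table 11). A patient who stops early with nothing later in the window would be shown with no change, when no on-treatment value exists. The SAP governs the NDA and MAA analyses (SAP 1), so its windows should be unambiguous.

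**Working it through.** **1. The windows side by side.**

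| | Baseline | On-treatment starts | Day 1 in both? |
|---|---|---|---|
| Protocol 11.2.10.3, 11.2.10.4 | up to and including the day of first dose | the day after first dose | No |
| SAP 3 with 14.2, 14.3 | up to and including the first dosing day | at first dose | By date: yes. By clock time: not for a predose sample |

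**2. What follows by date.** Let *b* be the Day 1 baseline and *x*₁ to *x*ₖ the later values in the window. The reported changes become

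- change to maximum = max(max *x* − *b*, 0)
- change to minimum = min(min *x* − *b*, 0)

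The first cannot be negative and the second cannot be positive. With k = 0, the maximum, minimum and last value all equal *b*, and every change is 0. Where grading runs in one direction, the worst on-treatment grade cannot be better than the baseline grade.

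**3. Size.** The documents give no figure for this, so there is none to reproduce. The inputs here are assumptions: *b* and the *x* values are independent normal with unit SD and no drug effect, and k is illustrative. Write E(k) for the expected maximum of k standard normal values. Without the overlap, mean change to maximum is E(k). With it, the mean is E(k+1), because *b* joins the set. The inflation is E(k+1) − E(k), and *b* is itself the maximum with probability 1/(k+1).

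| Later values k | E(k) | E(k+1) | Inflation (SD) | Baseline is the maximum |
|---|---|---|---|---|
| 1 | 0.000 | 0.564 | 0.56 | 50% |
| 2 | 0.564 | 0.846 | 0.28 | 33% |
| 3 | 0.846 | 1.029 | 0.18 | 25% |
| 5 | 1.163 | 1.267 | 0.10 | 17% |
| 12 | 1.629 | 1.668 | 0.04 | 8% |

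Change to minimum is shifted downward by the same amounts. A simulation of 400,000 patients agrees to within 0.003 SD.

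**4. Sensitivity.**

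- *Correlation within patient.* With exchangeable correlation ρ, the inflation in total-SD units is multiplied by √(1 − ρ). For k = 2, 0.282 × √0.5 = 0.20 at ρ = 0.5, and 0.282 × √0.3 = 0.15 at ρ = 0.7.
- *A drug-induced rise of 1 SD.* Bias in change to maximum falls to 0.20 (k = 1), 0.07 (k = 2) and 0.02 (k = 5). Bias in change to minimum grows to −1.20, −0.77 and −0.40 for the same k.

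**The case against.** The strongest objection is that, read literally, the SAP may have no overlap for scheduled samples. Its window runs from the first dose, and a sample drawn before that dose lies outside it. The SAP also knows how to write a date rule: SAP 14.1 defines treatment-emergent events by onset date relative to the date of first dose, while 14.2 and 14.3 do not mention dates. A reader might infer that Day 1 values certainly count twice, and the documents do not support that.

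They do not rule it out either. The baseline is defined by day, the adjacent adverse-event window is applied by date, and recording of draw time relative to dose is described only for PK samples (Protocol 9.8.3.2). A programmer could reasonably work by date, and the two readings give different tables.

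Four limits on the size also stand:

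- Not every patient has a Day 1 value, because Day 1 procedures may be omitted if done within the previous 3 days in screening (Protocol Tables 10 and 11).
- The largest figures need few later samples. Phase 2 fasting glucose is scheduled five times after Day 1 by Cycle 2 Day 15, so small k describes only very early stoppers there.
- A reader might infer that the overlap materially overstates glucose increases. The protocol says the drug raises glucose in some patients, and under such a rise the bias in change to maximum is small (0.02 SD at k = 5 with a 1 SD rise).
- The End of Treatment visit, 28 ± 7 days after last dose, gives some early stoppers a later value. Because it can fall after the 28-day limit, it does not do so for all.

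**Conclusion.** The point holds as an undocumented ambiguity with a possible bias. The SAP dropped the protocol's non-overlapping window, kept a baseline that includes Day 1, and did not record the change. If the window is applied by date, patients with a predose Day 1 value have it counted on both sides.

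The inflation of mean change to maximum, about 0.28 SD at 2 later samples falling to 0.04 SD at 12, is an illustration that rests on assumed independence and no drug effect. Correlation between a patient's values makes it smaller in total-SD units. A drug-induced rise makes it smaller for the maximum but makes the distortion of change to minimum larger. If the window is applied by clock time, predose samples cause no bias.

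The exposed outputs are descriptive laboratory and vital-sign summaries, worst-grade shift tables and glucose threshold counts. Response rate, duration of response and the separately defined ECG categories in SAP 14.4 do not use this window. The severity is low.

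**What to change.** In SAP 14.2 and 14.3, restore the protocol's definition: the on-treatment period runs from the day after first dose to 28 days after last dose. That is one sentence in each section. It needs no new data, and no entry in SAP 15 because the SAP would again match the protocol.

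The small cost is that any post-dose value taken on Day 1 is left out of the on-treatment summaries. If the sponsor prefers to keep the start at first dose, the SAP should say that predose values are baseline only and post-dose values on-treatment only, and list the departure in SAP 15. That option needs collection times for laboratory samples and vital signs, and the documents do not show that these are recorded.
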